9.2 Exploratory Analyses

In exploratory analyses, we will apply standard mediation analysis to explore separately whether symptom management or self-efficacy mediates the relationship between arm assignment and adherence. We will conduct multivariable regression to explore the following: (1) if arm assignment has an effect on symptom management or self-efficacy, (2) if either of these intermediate outcomes has an effect on daily adherence; (3) if arm assignment has an effect on daily adherence, or (4) if the effect of arm assignment on daily adherence shifts when either of these intermediate outcomes is added to the model. Rejecting the null for all four hypotheses will be necessary to support either symptom management or medication self-efficacy as a mediator. We will use a modified Sobel test for significance testing. Additionally, we will explore for potential effect modification across different patient subgroups based on patient demographics, health literacy, social determinants of health, clinical characteristics, and other factors. We will fit multivariable regression models with intervention, moderator, and interaction terms to assess potential effect modification based on significance of the interaction term. As planned analysis, we will also explore mortality differences between study arms at 6- and 12-month follow-up using data collected passively from the EHR (as outlined in the consent form).

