5.5 Sample Size and Accrual

Aim 1. The study sample will be drawn from adults seeking cancer care at the University of Pennsylvania's Abramson Cancer Center (ACC). Across recruitment sites, approximately 215 patients with lung cancer had orders for one of the included oral targeted therapies from January-September 2020. For this study, we will include both patients who have new prescriptions (after study launch) and patients previously taking these medications in 2020 (and who continue to take these medications at the time of eligibility assessment). Based on preliminary studies with Penny, we conservatively estimate that $\geq 40\%$ of patients approached will be eligible and consent to participate in this study. Of the 215 patients who started taking these medications in 2020 and estimated number of new starts during the study enrollment period (estimated 25 new starts per month), we anticipate that we will reach our target sample size of 170 in approximately 9-12 months (enrolling an estimated 85 patients who are currently taking these medications and 10 patients monthly who are new medication starts across the enrollment period). Allowing for a 15% loss to follow up, 72 participants will remain in each arm ($n=144$). Our full sample will provide 80% power to detect minimum effect of 20.9% or greater between the intervention and control group (assuming previously observed 65.5% adherence rate in controls and using fisher's exact test⁷), an effect size that is clinically significant and appropriate for this pilot stage of research.

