5.7 Participant Remuneration

In recognition of time needed to complete data collection surveys and the importance of retaining the MEMS caps, incremental remuneration will be provided to patients (\$25 at each time point) for total of \$75. All enrolled patients will be asked to complete a brief baseline survey (T0) and will receive \$25 upon completion of the baseline survey. Additionally, all patients will be re-contacted approximately 6 weeks after enrollment (T1) and after study completion (12 weeks from study start date; T2) to conduct two follow-up surveys. Patients who complete the midpoint (T1) survey will receive an additional \$25 upon survey completion. Patients will receive the final \$25 upon return of the electronic monitoring cap to the study team. If patients do not complete any additional surveys beyond baseline and do not return the electronic monitoring cap, they will not receive any additional remuneration beyond the initial \$25. Patients who do not complete the baseline survey will not be enrolled and not provided with any remuneration.

Patients will receive remuneration through issuance of GreenPhire ClinCards that will be mailed to participants within 10 days of enrollment and completion of baseline survey. These ClinCards can be used in the same manner as a credit card. ClinCards can be re-loaded remotely with additional funds by study team members after completion of study activities. Given the amount of participant remuneration, we are requesting a waiver of collection of social security numbers for the ClinCards.

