8.2 Assessment Procedures

MEMS Caps. Adherence data will be assessed via MEMS caps, which capture a date and time stamp each time the pill bottle is opened. MEMS caps are considered the gold standard of objective adherence measurement over other methods of adherence monitoring,^{31,32} and have been used successfully in previous studies of oral anticancer agents.^{5,25} MEMS data will be scanned to a secure web portal by research staff at the time of clinic appointments. All participants will receive MEMS cap(s) regardless of study assignment. Participants will be instructed to use this system for storage throughout the study, and to log any bottle openings for purposes other than pill ingestion (e.g., to check remaining supply) in a daily journal. After patients complete the baseline survey, a study team member will mail the MEMS Caps directly to the patients with instructions on how to install the MEMS cap. Patients will be contacted by phone approximately 7-10 days after the MEMS cap is mailed to them to confirm receipt and answer any questions. Patients will be instructed to begin using the MEMS cap the day immediately following the phone call as this will be their study start date.

Online Surveys. Trial participants (Aim 1) will be asked to complete online surveys at three timepoints: baseline assessment (T0) will occur at time of enrollment, followed by mid-point assessment approximately 6 weeks later (T1), and final assessment occurring within 2 weeks of trial completion (T2). Data will be captured via REDCap, a secure, web-based application for collecting and managing survey data³³. For REDCap data, patients will receive individualized links to each survey and will be contacted up to three times by email, text message, and/or phone to complete each survey. To increase data completion and study retention incremental compensation will be provided to patients. Specific measures to be assessed in the survey are described below.

Medical Record Data: Medical record data from enrolled patients will be abstracted across the study period to evaluate diagnostic and treatment changes, clinical characteristics, and healthcare utilization. We will also use medical record data to identify and recruit potentially eligible patients as outline in the HIPAA waiver.

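### Section 9.2 makes a significant total effect necessary for mediation, so true mediators are supported less often than with an interval for the indirect effect (exploratory, minor)

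*Combined protocol and SAP*

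**What the plan says.** Section 9.2 (Exploratory Analyses) plans a separate mediation analysis for symptom management and for medication self-efficacy. It lists four questions to be answered by multivariable regression: whether arm affects the mediator, whether the mediator affects daily adherence, "3) if arm assignment has an effect on daily adherence", and "4) if the effect of arm assignment on daily adherence shifts when either of these intermediate outcomes is added to the model".

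The decision rule follows: "Rejecting the null for all four hypotheses will be necessary to support either symptom management or medication self-efficacy as a mediator". The list joins its last two items loosely with the word or, but this sentence makes the rule a conjunction of all four.

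The section adds: "We will use a modified Sobel test for significance testing". It does not say that this test replaces the four-step rule, and it states no interval for the indirect effect.

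Section 5.5 gives the number of patients expected in the analysis: "Allowing for a 15% loss to follow up, 72 participants will remain in each arm".

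**The concern.** The third hypothesis is the total effect. An indirect effect can be present, and estimable, when the total effect is too small or too imprecise to reach significance. Making total-effect significance a condition therefore discards evidence about the pathway for a reason unrelated to the pathway.

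The Study Abstract (section 2) hypothesises that the chatbot works through symptom management and other determinants of behaviour, and section 9.2 is where that is examined. Section 9.1 also wants the results to inform later studies. If the total effect is moderate, the likely report is that neither mediator was supported, even where the same data could show an indirect effect and its precision. What is at stake is an exploratory conclusion about mechanism, not the primary comparison.

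**Working it through.** **Inputs from the documents.** 72 per arm, 144 in all (section 5.5; 170 × 0.85 = 144.5). Control adherence 65.5%, detectable difference 20.9 points, 80% power, Fisher's exact test (section 5.5). No mediator path sizes and no power for mediation are given. Two-sided 5% is assumed throughout.

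**1. The plan's own power figure.** 65.5% + 20.9 points = 86.4%. Exact power of Fisher's test with 72 per arm is 80.03%, so the stated 80% reproduces. This is for the ≥95% classification, not daily adherence, so it only indicates the total-effect power to expect. With about half the effect (65.5% against 76%), a simulated logistic Wald test has about 29% power.

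**2. The cap.** For any data model, P(all four rejected) ≤ P(hypothesis 3 rejected). This needs no assumption.

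**3. Size in an assumed linear model.** Mediator M = a·arm + e₁. Outcome Y = c′·arm + b·M + e₂. Unit error SDs, a = 0.5, b = 0.4.

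- Total effect = c′ + ab = c′ + 0.20. Its SE = √[(1 + b²) × 2/72] = √(1.16 × 0.02778) = 0.1795.
- For c′ = 0, 0.14 and 0.30 the total effects are 0.20, 0.34 and 0.50, so z = 1.11, 1.89 and 2.79. Power ≈ Φ(z − 1.96) = 20%, 47% and 80%.
- Arm to mediator: SE = √(2/72) = 0.1667, z = 3.0, power ≈ Φ(1.04) = 85%.
- Mediator to outcome: SE ≈ 1/√144 = 0.083, z = 4.8, power above 99%.

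Simulated results:

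| c′ | Total-effect power | Hypotheses 1–3 | Full rule, ordinary Sobel | Sobel alone | 95% Monte Carlo interval for ab |
|---|---|---|---|---|---|
| 0 | 20% | 19% | 18% | 77–78% | 85% |
| 0.14 | 47% | 43% | 40% | 77–78% | 85% |
| 0.30 | 79% | 70% | 65% | 77–78% | 85% |

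At c′ = 0.30 the total-effect condition accounts for about 15 of the 20 points lost (85% to 70%), and the Sobel approximation for the other 5 (70% to 65%). With strong paths (a = 0.8, b = 0.4, c′ = 0.4) the comparison is 97% against 99%.

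**4. Other outcome models, same direction.**

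- Binary outcome per patient, a = 0.5: at the design effect, with 30% to 65% of the effect mediated, the rule gives 56–75% and the interval 80–86%. At half the design effect, with 30% to 99% mediated, it is 5–27% against 29–86%.
- Daily adherence over 84 days, all tests on the proportion of adherent days, hypothesis 4 left out: requiring hypotheses 1–3 loses 5–15 points when the arm effect corresponds to +20.9 points in ≥95% status, 15–47 at +15, and 30–68 at +10.

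**5. False positives.** With no confounding, the interval wrongly excludes zero in about 5% of trials or fewer. With b = 0, a = 0.5 and an unadjusted common cause giving a mediator–outcome correlation of 0.2–0.3:

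| Method | Wrongly supports a mediator |
|---|---|
| Interval, unadjusted | about 56–81% |
| Four-step rule, no direct effect | about 2–4% |
| Four-step rule, direct effect 0.47 | about 31–57% |
| Interval, adjusted for covariates capturing 80% of the common cause | about 7–14% |

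Repeat runs moved these figures by up to about four points.

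**The case against.** The strongest objection is that the rule buys specificity. Both mediators arise after randomisation and are not randomised, so some confounding with adherence is likely. The last table shows that when arm has no direct effect, the four-step rule makes far fewer false claims than the interval, mainly because of the total-effect condition. Reverse influence points the same way. If adherence shifts the mediator by 0.2–0.3 SD per SD, an interval using the mid-study mediator with whole-period adherence wrongly excludes zero in 47–94% of trials, against 28–70% for the four-step rule. With adherence after the mid-study survey only, it is 12–89% against 5–64%.

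This stands as a cost of the change. It does not justify the rule as the only result. The protection largely goes once arm has a direct effect, and the rule does not address confounding; it only asks for one more significant test. Baseline adjustment does address it, to the extent that the covariates capture the common cause.

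It can also be said that the plan already tests the indirect effect, and that asking first whether arm and adherence are related is a coherent, conservative choice for an exploratory analysis. The first part is right: a reader might infer that section 9.2 ignores the indirect effect, and the Sobel sentence shows otherwise. What the rule withholds is support for a mediator. Part of the gap against an interval is Sobel conservatism.

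A reader might also count as errors the undefined modification of the Sobel test, the unstated survey wave for the mediator, the unlisted covariates, or the non-collapsibility of logistic coefficients. The documents do not support that. Section 8.3 places the survey items in appendices that are not reproduced, section 9.2 says multivariable regression and so does not exclude adjustment, and it names no link function.

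**Conclusion.** The concern holds as a minor point about an exploratory analysis. Because all four rejections are required, support for a mediator is capped by total-effect power, and that direction is certain. The size is not. In the assumed linear model the full rule supports a true mediator in about 18–65% of trials against about 85% for an interval, but the loss is only 2–3 points when all paths are strong. These figures rest on assumed path sizes, an ordinary Sobel test for hypothesis 4 and no confounding.

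Two stronger conclusions are tempting and not supported. One is that the interval is better in every respect: it is not when the mediator is confounded or influenced by adherence. The other is that the trial's main finding is at risk: the primary analysis and the sample size do not depend on section 9.2.

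**What to change.** In section 9.2:

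- Make the main exploratory mediation result the estimated indirect effect on the proportion of adherent days, with a 95% interval from a patient-level bootstrap or Monte Carlo method.
- Adjust the mediator and outcome models for the baseline value of the mediator, where it is collected at T0, and for a pre-listed set of baseline covariates. The section already names suitable sources for its subgroup work: "different patient subgroups based on patient demographics, health literacy, social determinants of health, clinical characteristics, and other factors".
- Report the total effect and the other step tests beside the indirect effect as description, not as necessary conditions.
- Label the result as hypothesis-generating, and as dependent on no unmeasured mediator–outcome confounding and no influence of adherence on the mediator.

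The cost is a change of wording and a modest amount of extra analysis on survey and MEMS data already planned. The simple yes/no rule is lost. The revised text should say openly that the interval can exclude zero through confounding more often than the four-step rule would, and that adjustment reduces this risk without removing it.

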9.3 Qualitative Analyses (Aim 2)

We will use convergent mixed-methods analysis to explore multilevel factors shaping acceptability, effectiveness, and implementation of Penny. The constant comparative method, guided by grounded theory, will be used to inductively explore emergent themes and deductively identify *a priori* domains of interest (guided by the five CFIR domains and IMB model) within and across interviews. Two trained coders will first independently read each transcript to identify themes within each domain. We then will use this list to develop a coding dictionary and apply it to subset of the data. We will measure inter-rater reliability to document and improve coding consistency. Once high reliability is achieved ($\kappa > 0.7$), we will apply the full coding dictionary to the interview data using NVivo (computer-assisted qualitative analytic software), and produce thematic reports summarizing our findings by each domain and sub-theme. Survey data will be analyzed descriptively. Qualitative and quantitative data will be analyzed and triangulated using a concurrent mixed-methods approach.⁴⁵

10.2 Regulatory Approvals

The University of Pennsylvania IRB will serve as the IRB of record for this trial. The study has a dedicated project manager who will ensure that the most current version of the study protocol and supplementary materials are added into Penn's Human Subjects Electronic Research Application (HS-ERA) system and the Abramson Cancer Center's Clinical Trials Scientific Review and Monitoring Committee. The project manager will additionally be responsible for submitting protocol-wide modifications and for reporting any deviations, exceptions, and reportable events within required timeframes to the co-PIs and IRB. A formal closure request will be submitted once study activity has been completed and there is no further access to identifiable subject data for research purposes.

10.3 Data Confidentiality

Paper-based records will be stored in a secure location and only be accessible to personnel involved in the study. Computer-based records will be stored on a secure UPHS server, within PennChart, or on the third party development company, Memora Health's, secure and HIPAA compliant platform. The technical components of this platform have been reviewed by Penn Medicine IS Security and was approved for PHI. Select staff from Memora Health will have access to the Penny platform during the study, along with investigators that have been listed from the Penn Medicine. All Penn Medicine staff have completed their HIPAA security training and all co-PIs and key investigators have completed CITI Protection of Human Subjects Research Training.

Since this study will be done over text messaging, neither Penn Medicine nor Memora Health can guarantee the confidentiality of the information sent to a patient once it arrives on their phone. We will include this language in the consent form and it will be reviewed orally with patients at the time of consent.

10.4 Subject Confidentiality

How will confidentiality of data be maintained? Check all that apply.

- Paper-based records will be kept in a secure location and only be accessible to personnel involved in the study.
- Computer-based files will only be made available to personnel involved in the study through the use of access privileges and passwords.
- Prior to access to any study-related information, personnel will be required to sign statements agreeing to protect the security and confidentiality of identifiable information.
- Whenever feasible, identifiers will be removed from study-related information.
- A Certificate of Confidentiality will be obtained, because the research could place the subject at risk of criminal or civil liability or cause damage to the subject's financial standing, employability, or liability.

- A waiver of documentation of consent is being requested (for interview participants only), because the only link between the subject and the study would be the consent document and the primary risk is a breach of confidentiality. (This is not an option for FDA-regulated research.)
- Precautions are in place to ensure the data is secure by using passwords and encryption, because the research involves web-based surveys.
- Audio and/or video recordings will be transcribed and then destroyed to eliminate audible identification of subjects.
- Other (specify):

Aim 1. All patients participating within the study will be made aware of all risks related to subject confidentiality, including the minimum amount necessary of personal data being sent to a third-party (Memora Health, with whom we do have a Business Associate Agreement and has previously been approved by Penn Medicine IS Security) and the security limitations around receiving text messages. This will be stated in the consent form and reviewed verbally with each patient during consent discussion. All other data that contains subject information will be either physically securely stored or be protected on secure UHPS servers, REDCap, or within the patient's medical record.

Aim 2. The most substantial risk to all participants includes potential violation of confidentiality. To help protect against this risk, we will use the following safeguards: 1) all data including but not limited to consent forms, questionnaire data, audio files from interviews, notes from medical record review, and qualitative transcripts will be kept in a password-protected file or locked cabinet; 2) participant identity will be masked using unique participant IDs and stored on a password-protected master list to which only the PI and approved research staff will have access; 4) any paper questionnaire data will be collected and entered into secure REDCap and then destroyed after study completion; 6) any protected health information received from the participants will be housed on secure UPHS servers and only accessible by the PIs and approved research members; and 7) all statistical or qualitative analytic files will be identified only with participant IDs and not contain any protected health information (all identifiable data will be recoded (e.g. true dates will be turned into days from index date) prior to including it into the analytic datasets). For interviews, all identifying information will be redacted from the transcription. Audio files will be kept on the UPHS secure server and only shared with HIPAA-compliant transcriptionists. Upon completion of the study, audio files will be destroyed in accordance with IRB policy. In manuscripts, analytic datasets, or summation or reporting of data, no PHI will be used.

10.5 Subject Privacy

For trial participants, enrollment will include a detailed description of the voluntary nature of participation, study procedures, risks and potential benefits. The enrollment procedures will allow the opportunity for potential participants to ask questions and review with family and friends prior to making a decision to participate. Participants will be informed that they may drop out at any time, without affecting their medical care or cost of their care. They will be told they may or may not benefit directly from the study and that all information will be kept strictly confidential, except as required by law. Subjects will be given a copy of the consent form. All efforts will be made by study staff to ensure subject privacy.

For patient and provider interviews, to protect subject privacy, the consent process and interviews will take place in a private location or by phone. During the consent process, we will inform participants that they have to the right to skip any question that they prefer not to answer and can withdraw from participation at any time.

10.6 Data Disclosure

The following entities, besides the members of the research team, may receive protected health information (PHI) for this study:

- Memora Health, the company we are working with to develop Penny and who possesses the AI chatbot technology. Memora Health has a Master Services Agreement contract in place with Penn Medicine, have previously signed a BAA and has been reviewed and approved to receive PHI by Penn Medicine's IS Security Team.
- The Office of Human Research Protections at the University of Pennsylvania
- Federal and state agencies (examples – Department of Health and Human Services, the National Institutes of Health, and/or the Office for Human Research Protections), or other domestic or foreign government bodies if required by law and/or necessary for oversight purposes.

